5.4.4. Dosing Interruptions/Delays due to Non-Related Events

If participants require treatment interruption for reasons other than treatment-related toxicity (eg, surgery) lasting >4 weeks, treatment resumption should be decided in consultation with the Sponsor.

In the event of active SARS-CoV2 infection confirmed (positive by regulatory authority-approved test) or presumed (test pending/clinical suspicion), the following criteria apply:

- For symptomatic participants with active SARS-CoV2 infection, investigational treatment should be delayed for at least 14 days from start of symptoms.
- This delay is intended to allow resolution of symptoms of SARS-CoV2 infection.
- Prior to restarting treatment, the participants should be afebrile for 72 hours and SARS-CoV2-related symptoms should have recovered to \leq Grade 1 for a minimum of 72 hours.
- Discuss with the Sponsor prior to restarting treatment.
- Consider potential drug-drug interactions (as described per study protocol) for any concomitant medication administered for treatment of SARS-CoV2 infection.

5.4.5. Dose Reductions

Following dose interruption or cycle delay due to toxicity, the investigational product(s) may need to be reduced when treatment is resumed.

No specific dose adjustments are recommended for Grade 1/2 treatment-related toxicity, unless otherwise specified. However, investigators should always manage their participants according to their medical judgment based on the particular clinical circumstances.

5.4.5.1. AdC68 Dose Reductions

Changes in the dose levels for AdC68 will be discussed with the sponsor. Dose reduction of adenovirus by 1 dose level may be allowed in Part 1 depending on the type and severity of toxicity encountered. No dose level reduction is allowed in Part 2. All dose modifications/adjustments must be clearly documented in the participant's source notes and CRF.

Once a dose has been reduced for a given participant, all subsequent cycles should be administered at that dose level for that participant, unless further dose reduction is required. Dose re-escalation for adenovirus is not allowed.

Table 4. AdC68 Available Dose Levels (Part 1)

Dose Level	AdC68*
+1	6×10^{11} VP
Starting	2×10^{11} VP

Table 5. AdC68 Available Dose Levels (Part 2)

Dose Level	AdC68*
Starting	6×10^{11} VP
-1	2×10^{11} VP

Table 6. Dose Modifications for AdC68 Related Toxicity

Toxicity	Grade 1/2	Grade 3	Grade 4
Non-hematologic (other than irAE management described in Appendix 5)	Continue at the same dose level.	Withhold dose until toxicity is Grade ≤ 1 , or has returned to baseline, then resume treatment at the same dose level or reduce the dose by 1 level at the discretion of the investigator*.	Discontinue treatment.
Hematologic	Continue at the same dose level.	Withhold dose until toxicity is Grade ≤ 2 , or has returned to baseline, then resume treatment at the same dose level.	Discontinue treatment.

* Nausea, vomiting, or diarrhea must persist at Grade 3 despite maximal medical therapy to require dose modification.

5.4.5.2. Tremelimumab Dose Reductions

Changes in the dose levels for tremelimumab will be discussed with the sponsor. A dose reduction of tremelimumab by 1 dose level (from 80 mg to 40 mg) may be allowed depending on the type and severity of toxicity encountered. In addition, an intermediate dose may be considered. Participants requiring a dose level lower than 40 mg will be discontinued from treatment and enter into the follow-up phase unless otherwise agreed between the investigator and sponsor. Algorithms for the management of suspected pulmonary,

gastrointestinal (GI), liver, endocrine, skin, neurological and renal toxicities have been developed (See [Appendix 5](#)). All dose modifications/adjustments must be clearly documented in the participant's source notes and case report form (CRF).

Once a dose has been reduced for a given participant, all subsequent cycles should be administered at that dose level, unless further dose reduction is required. Dose re-escalation for tremelimumab is not allowed.

Table 7. Tremelimumab Available Dose Levels (Part 1)

Dose Level	Tremelimumab
Starting	40 mg
+1	80 mg

Table 8. Tremelimumab Available Dose Levels (Part 2)

Dose Level	Tremelimumab
Starting	80 mg
-1	40 mg

Table 9. Dose Modifications for Tremelimumab Related Toxicity When Given in Combination with AdC68 and pDNA

Toxicity	Grade 1	Grade 3	Grade 4
Non-hematologic	Continue at the same dose level.	Withhold dose until toxicity is Grade ≤ 1 , or has returned to baseline, then resume treatment at the same dose level or reduce the dose by 1 level at the discretion of the investigator.*	Discontinue treatment.
Hematologic	Continue at the same dose level.	Withhold dose until toxicity is Grade ≤ 2 , or has returned to baseline, then resume treatment at the same dose level.	Discontinue treatment.

* Nausea, vomiting, or diarrhea must persist at Grade 3 despite maximal medical therapy to require dose modification.

5.4.5.3. Sasanlimab Dose Reductions

Events including, but not limited to, pneumonitis, colitis, creatinine and liver function test (LFT) elevation should be monitored carefully with this class of agents. Dose reductions may be required for sasanlimab, tremelimumab or potentially both compounds depending on the event and the severity of the toxicity. Dose reductions of sasanlimab from 300 mg to 130 mg may be allowed. In addition an intermediate dose may be considered. All dose modifications/adjustments must be clearly documented in the participant's source notes and CRF.

Table 10. Sasanlimab Available Dose Levels (Part 1)

Dose Level	Sasanlimab
Starting	130 mg
+1	300 mg

Table 11. Sasanlimab Available Dose Levels (Part 2)

Dose Level	Sasanlimab
Starting	300 mg
-1	130 mg

Algorithms for the management of suspected pulmonary, GI, liver, endocrine, skin, neurological and renal toxicities have been developed (See [Appendix 5](#)).

Participants requiring >4 weeks of dose interruption should be considered for discontinuation of treatment with sasanlimab. Participants may be allowed to resume dosing with the AdC68, pDNA and tremelimumab without sasanlimab for one dose with plans to resume sasanlimab at the next dosing time point if agreed upon by the investigator and sponsor. Participants who discontinue sasanlimab due to toxicity will be allowed to remain in the study and continue treatment with the other components.

The following serves as demonstrating general rules. Action may differ in specific cases based on evaluation by the investigator and the sponsor.

Table 12. Dose Modifications for Sasanlimab and/or Tremelimumab Related Toxicity

Toxicity	Grade 1	Grade 2	Grade 3	Grade 4
Non-hematologic	Continue at the same dose level.	For pneumonitis, endocrinopathy, colitis, creatinine, AST, ALT, or total bilirubin elevations, withhold dose until toxicity is Grade ≤ 1 , or has returned to baseline, then resume at the same dose level or reduce by 1 level (considering each compound separately) at the discretion of the investigator. For all other events, continue at the same dose level.	For pneumonitis, colitis, endocrinopathy, creatinine, AST, ALT or total bilirubin elevations, or pruritus discontinue treatment.** For all other events withhold dose until toxicity is Grade ≤ 1 , or has returned to baseline, then resume treatment at the same dose level or reduce the dose by 1 level (considering each compound separately) at the discretion of the investigator.* Treatment may resume with VBIR-2 with an interruption of sasanlimab for one dose at the discretion of the investigator.	Discontinue treatment.**
Hematologic	Continue at the same dose level.	Continue at the same dose level.	Withhold dose until toxicity is Grade ≤ 2 , or has returned to baseline, then resume treatment at the same dose level.	Discontinue treatment.**

* Nausea, vomiting, or diarrhea must persist at Grade 3 despite maximal medical therapy to require dose modification.

** For Grade ≥ 3 colitis or pneumonitis, discontinue treatment permanently. For any grade of myocarditis discontinue treatment permanently. For all other conditions participants may be allowed to remain in the study to receive the VBIR-2 2 after the toxicity is Grade ≤ 1 or returned to baseline, and only if agreed upon by the Investigator and Sponsor.

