5.4.1. Recommended Dose Modifications

Every effort should be made to administer investigational product on the planned dose and schedule.

In the event of significant toxicity, dosing may be delayed and/or reduced as described below. In the event of multiple toxicities, dose modification should be based on the worst toxicity observed. Participants are to be instructed to notify investigators at the first occurrence of any adverse symptom.

Dose modifications may occur in one of three ways:

- Within a cycle: dosing interruption until adequate recovery and dose reduction, if required, during a given treatment cycle;
- Between cycles: next cycle administration may be delayed due to persisting toxicity when a new cycle is due to start;

- In the next cycle: dose reduction may be required in a subsequent cycle based on toxicity experienced in the previous cycle.

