Appendix 5. Management of Immune-related Adverse Events (irAEs)

Management of irAEs including Myasthenia Gravis		
Gastrointestinal irAEs		
Severity of Diarrhea/Colitis (NCI-CTCAE v5.0)	Initial Management	Follow-up Management
Grade 1 Diarrhea: <4 stools/day over Baseline Colitis: asymptomatic	-Continue study treatment. -Symptomatic treatment (eg, loperamide).	-Close monitoring for worsening symptoms. -Educate patient to report worsening immediately. -If worsens: Treat as Grade 2, 3 or 4.
Grade 2 Diarrhea: 4 to 6 stools per day over Baseline; IV fluids indicated <24 hours; not interfering with ADL Colitis: abdominal pain; blood in stool	-Withhold study treatment. -Symptomatic treatment.	-If improves to Grade ≤ 1 : Resume study treatment. -If persists >5-7 days or recurs: Treat as Grade 3 or 4.
Grade 3 to 4 Diarrhea (Grade 3): ≥ 7 stools per day over Baseline; incontinence; IV fluids ≥ 24 h; interfering with ADL Colitis (Grade 3): severe abdominal pain, medical intervention indicated, peritoneal signs Grade 4: life-threatening, perforation	-Withhold for Grade 3. -Permanently discontinue study treatment for Grade 4 or recurrent Grade 3. -1.0 to 2.0 mg/kg/day prednisone IV or equivalent. -Add prophylactic antibiotics for opportunistic infections. -Consider lower endoscopy.	-If improves: -Continue steroids until Grade ≤ 1 , then taper over at least 1 month; resume study treatment following steroids taper (for initial Grade 3). -If worsens, persists >3 to 5 days, or recurs after improvement: -Add infliximab 5mg/kg (if no contraindication). -Note: infliximab should not be used in cases of perforation or sepsis.

Dermatological irAEs		
Grade of Rash (NCI-CTCAE v5.0)	Initial Management	Follow-up Management
Grade 1 to 2 Covering \leq 30% body surface area	
 -Continue study treatment. -Symptomatic therapy (for example, antihistamines, topical steroids). 	
 -If persists >1 to 2 weeks or recurs: 
 -Withhold study treatment; -Consider skin biopsy. -Consider 0.5-1.0 mg/kg/day prednisone or equivalent. Once improving, taper steroids over at least 1 month, consider prophylactic antibiotics for opportunistic infections, and resume study treatment following steroids taper. -If worsens: Treat as Grade 3 to 4.

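### For diarrhea without colitis, Table 12 and Appendix 5 differ on whether to hold treatment at Grade 2 and at treatment-responsive Grade 3, and nothing says which governs

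*Protocol*

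**What the plan says.** **Table 12 (Section 5.4.5.3)** covers toxicity related to sasanlimab, tremelimumab or both. Its Grade 2 non-hematologic cell names the events that lead to withholding. Colitis is named and diarrhea is not. For the rest: "For all other events, continue at the same dose level". Its Grade 3 cell says of unlisted events "For all other events withhold dose until toxicity is Grade" 1 or less, or back to baseline, and carries footnote *: "Nausea, vomiting, or diarrhea must persist at Grade 3 despite maximal medical therapy to require dose modification". The same footnote stands under Table 6 (AdC68) and Table 9 (tremelimumab with AdC68 and pDNA).

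**Section 5.4.1** lists what counts as a dose modification. The first form is "Within a cycle: dosing interruption until adequate recovery and dose reduction, if required, during a given treatment cycle".

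**Appendix 5**, gastrointestinal rows, grades diarrhea alongside colitis. Its Grade 2 entry is "Grade 2 Diarrhea: 4 to 6 stools per day over Baseline", and the action is "Withhold study treatment. -Symptomatic treatment". If this lasts more than 5 to 7 days or recurs, it is treated as Grade 3 or 4. For Grade 3 the entry is "Withhold for Grade 3", with steroids and no persistence condition. Grade 4 or recurrent Grade 3 is a permanent stop.

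**Section 5.4.2** interrupts all components for Grade 3 or 4 toxicity that may be treatment-related, and for Grade 2 that is intolerable despite supportive care.

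**Linking text.** Section 5.4.5 recommends no specific adjustment for Grade 1 or 2 treatment-related toxicity except where stated elsewhere. Sections 5.4.5.2 and 5.4.5.3 both point to Appendix 5 for suspected gastrointestinal toxicity. Table 12 is introduced as general rules from which the investigator and sponsor may depart in specific cases.

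**The concern.** A site facing diarrhea without colitis has several protocol passages to consult, and they do not give the same answer. If Table 12 is followed, both antibodies continue through Grade 2, and at Grade 3 a hold is not mandatory until maximal medical treatment has failed. If Appendix 5 is followed, all study treatment is withheld at Grade 2 and at Grade 3, and steroids are started at Grade 3.

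Section 1.6.3 names diarrhea among the most common tremelimumab-related events, so the instruction concerns an expected toxicity. Adverse events are a primary endpoint of Part 2 (Section 2.2), which enrolls about 30 participants (Section 9.3) without a data monitoring committee (Section 9.7). If sites resolve the ambiguity differently, exposure to the regimen and the handling of a safety event would differ between participants for reasons unrelated to their condition.

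**Working it through.** The plan gives no figure here to reproduce. The check is a comparison of instructions by grade, for diarrhea without colitis.

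| Situation | Table 12 with footnote * | Appendix 5 | Section 5.4.2 | Agreement |
|---|---|---|---|---|
| Grade 1 | Continue | Continue | Not addressed | Yes |
| Grade 2 | Continue (unlisted event) | Withhold | Interrupt only if intolerable despite supportive care | No |
| Grade 3, responds to treatment | Modification not required | Withhold, steroids | Interrupt | No |
| Grade 3, persists despite maximal treatment | Withhold | Withhold, steroids | Interrupt | Yes, on the hold |
| Grade 4 | Discontinue; return possible by agreement | Discontinue permanently | Interrupt | Yes, on stopping |

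**Does footnote * reach holds as well as dose reductions?** Yes. Section 5.4.1 counts a dosing interruption as a modification.

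**Where does each conflict come from?** In Table 12 the asterisk sits in the Grade 3 cell. The Grade 2 conflict comes from the Grade 2 cell text, and the footnote merely agrees with it. The Grade 3 conflict comes from the footnote, and it is between a hold that is called for and a hold that is not required.

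**Is there an order of precedence?** Table 6 excludes events managed under Appendix 5 from its non-hematologic row. Tables 9 and 12, which cover the checkpoint antibodies, carry no such exclusion.

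**How far apart can the paths run at Grade 3?** Under Appendix 5, steroids continue until Grade 1 or less, are tapered over at least 1 month, and treatment resumes after the taper. Assume a month of 28 days, as the Part 2 maintenance schedule defines it, and let *s* be the days from the start of the hold to Grade 1 or less.

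- Hold ≥ *s* + 28 days. Active-phase doses are 28 days apart (Table 2), so, ignoring visit windows, such a hold covers at least one scheduled dosing day. The footnote path may miss none.
- Resumption after more than 2 weeks (14 days) of interruption needs obvious clinical benefit and sponsor agreement (text preceding Section 5.4.4). Counted from the start of the hold, 28 > 14, so this limit is always exceeded.
- The protocol does not say when counting starts. If it starts at the missed dose, and diarrhea began *t* days after the last dose, the minimum delay is (*t* + *s* + 28) − 28 = *t* + *s* days. With illustrative values *t* = 3 and *s* = 5 it is 8 days, below the limit. With *t* = 20 and *s* = 5 it is 25 days, above it.

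**The case against.** The best defense is that this is a general table plus a specific algorithm. Appendix 5 is titled for immune-related events. Table 12 covers any toxicity attributed to either antibody and is introduced as general rules. Section 5.4.5 leaves room for exceptions at Grade 2, and the Appendix 5 hold can be read as one. Section 5.4.2 agrees with Appendix 5 on holding at Grade 3. A careful investigator could combine these into one consistent practice.

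Much of this stands, and it narrows the point. It does not close it, because none of these sentences says which passage prevails. Permission to depart in specific cases does not settle the default. Table 12 covers the antibodies for which immune-related diarrhea is most to be expected, yet it lacks the exclusion that Table 6 has.

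Two further objections also have force:

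- **Timing.** With 4-weekly dosing, a Grade 2 episode that resolves between doses need not change dosing under either passage. This holds for brief, non-recurrent episodes. Appendix 5 escalates one that lasts beyond 5 to 7 days.
- **Table 9.** Its title fits the Part 1 cohort without sasanlimab. Part 1 is complete, so in Part 2 it matters at most for participants who stop sasanlimab.

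A reader might go further and infer that the footnote instructs sites to keep dosing through Grade 3, that the passages are opposed for every episode, or that the conflict will arise often. The documents support none of these. The footnote says when modification is required and does not bar an earlier hold. Section 1.6.3 rests largely on intravenous tremelimumab and gives no diarrhea rate by grade, and the documents as released give no rate for the 80 mg subcutaneous regimen.

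**Conclusion.** The inconsistency is real and limited. For diarrhea without colitis, the instructions diverge at Grade 2 (continue against withhold) and at Grade 3 that responds to treatment (hold not required against hold). They agree on whether to dose at Grade 1, at Grade 3 persisting despite maximal treatment, and, on stopping, at Grade 4. A participant in one of the two divergent situations at a dosing visit could be dosed or held depending on the passage followed. At Grade 3, the Appendix 5 path covers at least one scheduled dosing day in the active phase and may bring the 2-week limit into play.

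The conclusion rests on three readings: that diarrhea, being unlisted, belongs with the other events in Table 12; that Section 5.4.1 defines modification for the footnote; and that in Section 5.4.2 the supportive-care condition attaches to Grade 2 only. The Grade 2 conflict does not depend on the last two.

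Neither the number of participants affected nor any effect on the Part 2 adverse-event results can be estimated from the documents. The point calls for correction because it concerns a safety instruction, not because a distortion of results has been shown. Which rule is clinically right is not judged here.

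**What to change.** Reconcile the following so that one rule applies to diarrhea without colitis at Grade 2 and one at Grade 3:

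- Section 5.4.2 (interruption criteria) and Section 5.4.5 (the Grade 1/2 statement);
- the Table 12 Grade 2 non-hematologic cell;
- footnote * under Tables 6, 9 and 12;
- the gastrointestinal rows of Appendix 5.

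Then state which passage governs when diarrhea may be immune-related. If the intent is that Appendix 5 takes over, repeating Table 6's exclusion in Tables 9 and 12 would say so. If the intent is different, the text should say that instead. The sponsor's clinical team must choose the rule. It would also help to state whether an interruption is counted from the start of the hold or from the first missed dose.

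The cost is protocol wording in an amendment or clarification letter, with notice to sites. No procedures, visits or participants are added, and the statistical analyses do not change.

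### A first Grade 3 colitis is a permanent stop in Table 12 but withhold-and-resume in Appendix 5, and nothing says which governs

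*Protocol*

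**What the plan says.** **Table 12, Section 5.4.5.3.** The Grade 3 non-hematologic cell reads "For pneumonitis, colitis, endocrinopathy, creatinine, AST, ALT or total bilirubin elevations, or pruritus discontinue treatment". The double-asterisk footnote attached to it makes the stop permanent: for Grade 3 or higher "colitis or pneumonitis, discontinue treatment permanently", and likewise for myocarditis of any grade. It then opens a route back, if the investigator and sponsor agree: "For all other conditions participants may be allowed to remain in the study to receive the VBIR-2". Colitis is outside that route. The table is introduced with this caveat: "The following serves as demonstrating general rules. Action may differ in specific cases based on evaluation by the investigator and the sponsor".

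**Appendix 5, gastrointestinal events.** The Grade 3 to 4 row covers diarrhea and colitis together and describes Grade 3 colitis as "severe abdominal pain, medical intervention indicated, peritoneal signs". Initial management is to withhold for Grade 3 and "Permanently discontinue study treatment for Grade 4 or recurrent Grade 3". For an event that improves, follow-up management is to taper steroids over at least one month and then "resume study treatment following steroids taper (for initial Grade 3" (the source closes its parenthesis there).

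**Table 9, Section 5.4.5.2.** For Grade 3 non-hematologic toxicity related to tremelimumab, the dose is withheld until recovery, "then resume treatment at the same dose level or reduce the dose by 1 level at the discretion of the investigator". Colitis is not excepted. The table's title refers to tremelimumab given with AdC68 and pDNA.

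**AdC68, Section 5.4.5.1.** The text rules out any AdC68 dose reduction in Part 2. Table 5, headed for Part 2, nevertheless lists a -1 level of 2×10^11 VP, and Table 6 offers a one-level reduction without limiting it to Part 1.

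**The concern.** The two instructions address the same event at the same grade and start from opposite ends. Under Table 12 the participant is finished with treatment. Under Appendix 5 the participant is expected back once the steroids are tapered. An investigator who follows Appendix 5 as written is preparing to re-expose someone whom Table 12 bars.

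The cross-references make this easy to do. Sections 5.4.5.2 and 5.4.5.3 both direct the reader to Appendix 5 for gastrointestinal toxicity, so a site that follows the pointer lands on the more permissive page. Section 5.4.5.3 also says that participants who stop sasanlimab for toxicity may continue the other components, which include tremelimumab.

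The event is foreseeable. Section 1.6.5 reports more diarrhea and colitis with the higher tremelimumab dose when combined with durvalumab. What is at stake is participant safety and consistent handling of a serious immune toxicity.

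**Working it through.** The check is mainly a comparison of texts, with one short piece of arithmetic.

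**Step 1. Does Appendix 5 follow the footnote for the conditions the footnote singles out?**

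| Condition | Table 12 footnote | Appendix 5 | Agree? |
|---|---|---|---|
| Pneumonitis, Grade 3 or higher | Permanent stop | Permanent stop for Grade 3 to 4 | Yes |
| Myocarditis, any grade | Permanent stop | Permanent stop once judged immune-mediated | Yes |
| Colitis, Grade 3, first episode | Permanent stop | Withhold, taper, resume | No |
| Colitis, Grade 4 or recurrent Grade 3 | Permanent stop | Permanent stop | Yes |

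Only the first episode of Grade 3 colitis diverges. This looks like one row that was not aligned, not a different policy in the appendix.

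**Step 2. Does any text rank the two?** I found none. The pointers to Appendix 5 in Sections 5.4.5.2 and 5.4.5.3 give no order of precedence. Table 6 does defer to Appendix 5 for immune-related events, but it governs AdC68 only. The caveat above Table 12 allows departures case by case and does not say which of two opposite defaults is the starting point.

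**Step 3. How far could the Appendix 5 route run without the sponsor?** Inputs: a taper of at least 1 month (Appendix 5); a month of 28 days (Part 2 maintenance schedule, applied here to the taper as an assumption); a 2-week limit on interruption for treatment-related toxicity (end of Section 5.4.3).

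- Shortest interruption on the Appendix 5 route: 28 days, plus the time to reach Grade 1 or lower.
- Limit: 2 × 7 = 14 days.
- Excess: 28 − 14 = at least 14 days.

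The Appendix 5 route therefore always passes the limit. Beyond it, permanent discontinuation should be considered, and resumption requires obvious clinical benefit and agreement between investigator and sponsor.

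**Step 4. Does Table 9 add a third rule?** Only marginally. Its title omits sasanlimab, Part 1 enrolment is complete, and every Part 2 participant starts on sasanlimab. It could matter for someone who has stopped sasanlimab for another reason. Table 12's title covers toxicity related to sasanlimab, tremelimumab or both, so the two tables overlap there.

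**Step 5. AdC68.** The Section 5.4.5.1 text and Table 5 cannot both hold for Part 2. The only dose affected is the second priming dose, on Cycle 2 Day 1. Changes must be discussed with the sponsor. The column heading of Table 5 carries an asterisk with no visible note, so a lost explanation cannot be excluded.

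**The case against.** The strongest reply is that the contradiction has little practical effect. Step 3 shows that resumption after a one-month taper cannot proceed on the site's word alone. Section 3.4 adds that Part 2 events meeting the dose-limiting-toxicity grading criteria are taken promptly to the next safety meeting of sponsor and investigators. Grade 3 or higher non-hematologic major organ toxicity is one of those criteria (Section 3.2), so Grade 3 colitis would normally be reviewed there. Table 12 is itself a set of general rules. In practice both routes lead to a joint decision.

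Most of this stands, and it limits the weight of the point. A reader might infer that sites could re-treat a participant after Grade 3 colitis unaided; the documents do not support that. What the safeguards do not do is settle the starting instruction. Section 5.4.3 leaves return open by agreement, while the Table 12 footnote withholds the agreed route for colitis.

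Three other stronger readings are tempting and should be resisted.

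- That there is a three-way conflict with Table 9. Its title makes it mainly a rule for dosing without sasanlimab.
- That Grade 3 diarrhea is equally contradictory, because the Amendment 1 entry mentions diarrhea. The current text is broadly consistent: Table 12 leaves diarrhea among the events to be withheld and resumed, as does Appendix 5. A difference from an amendment log is not an error.
- That the harm can be expressed as doses or expected cases. The documents give no Grade 3 colitis rate for this regimen and do not say that delayed doses are forfeited.

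**Conclusion.** The conflict between Table 12 and Appendix 5 is real, is in the current text, and is confined to a first episode of Grade 3 colitis. It should be corrected, because the starting instruction for a serious immune toxicity ought not to depend on which page is read, and Section 9.7 provides for no data monitoring committee. Its size is modest: sponsor agreement and the joint safety discussion stand between the wording and any re-exposure. It has no effect on endpoints, sample size or analysis.

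The conclusion rests on reading the footnote's remaining-conditions clause as excluding colitis, which its wording requires, and on the absence of a precedence statement in the text available. That the permanent stop is the intended rule is an inference from the agreement for pneumonitis and myocarditis; the sponsor should confirm it. The AdC68 mismatch is minor and of low impact.

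**What to change.** 1. In the Appendix 5 gastrointestinal Grade 3 to 4 row, separate colitis from diarrhea and state that Grade 3 or higher colitis is a permanent discontinuation, as in Table 12. Leave the Grade 3 diarrhea rule as it is.
2. Add a line to Table 9 that Grade 3 or higher colitis follows Table 12.
3. Do not substitute a general sentence that the stricter instruction governs. Appendix 5 makes Grade 3 liver-test elevations a permanent stop, while Table 12 allows return by agreement, so such a sentence would also remove that route.
4. Minor: delete the -1 row of Table 5 and limit the one-level reduction in Table 6 to Part 1, unless the note behind the Table 5 asterisk explains the row.

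The cost is a few table cells in an administrative letter or protocol amendment. No extra participants, procedures or analyses are needed.
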